10.2 METHODS AND TIMING FOR ASSESSING, RECORDING, AND ANALYZING SAFETY PARAMETERS

10.2.1 UNANTICIPATED PROBLEMS

Unexpected Events (UE) will be recorded) and will include information such as the date of the event, when the study team was informed of this event, details of the event, when the IRB was notified. The IRB will be notified of each UE that may occur during the study.

The Office for Human Research Protections (OHRP) considers unanticipated problems involving risks to subjects or others to include, in general, any incident, experience, or outcome that meets all of the following criteria:

- unexpected (in terms of nature, severity, or frequency) given (a) the research procedures that are described in the protocol-related documents, such as the IRB-approved research protocol and informed consent document; and (b) the characteristics of the subject population being studied;
- related or possibly related to participation in the research (in the guidance document, possibly related means there is a reasonable possibility that the incident, experience, or outcome may have been caused by the procedures involved in the research); and
- suggests that the research places subjects or others at a greater risk of harm (including physical, psychological, economic, or social harm) than was previously known or recognized.

If an UE occurs the IRB will be notified and the study will be adjusted as needed to protect the health and safety of the participants. Depending on the nature of the UE, the research protocol, inclusion/exclusion criteria, and informed consent will be changed to reflect the possibility of this event reoccurring. During this time, no new participants will be recruited and the research procedures for currently enrolled participants will be stopped. Each UE will be recorded and reported throughout the study.

11 STATISTICAL PLAN

The statistician for this study is [name].

11.1 STATISTICAL ANALYSIS STRATEGIES

Outcome variables include:

Aim 1

- 1) motor-evoked potentials to measure corticospinal excitability (unit: uV)
- 2) TMS-evoked potentials to measure cortical excitability (unit: uV)

Aim 2

- 1) EEG spectral power in the theta-band (4-8Hz) averaged over frontal EEG channels to measure engaged brain network dynamics (unit: dB).
- 2) EEG spectral power in the alpha-band (8-12Hz) averaged over left frontal EEG channels to measure disengaged brain network dynamics (unit: dB).

For all analyses, outcome measures are analyzed as the difference from baseline metrics before the GTT. The repeated measures of primary outcome will be fitted into general linear mixed effect model where baseline measures (continuous), time of measures (categorical), treatment method (binary) and time by treatment as fixed effects, while the within-subject effect among different time point (0, 30, 60, 120, 180 minutes) is modeled as random intercept assuming autoregression model (AR(1)) as covariance structure. The two sided Wald-test of treatment method (fixed effect) between the verum GTT versus control GTT condition is our primary result of interest. We hypothesize a significant main effect for factor GTT but no effect for factor time nor the interaction of GTT by time. We hypothesize that verum-GTT will modulate corticospinal and cortical excitability. In case we do find a significant interaction of GTT by time, we will use post-hoc contrast test to compare the overall differences between verum-GTT versus control-GTT at each time point and correct for multiple comparisons using false discovery rate (FDR) method. All hypothesis tests that are observed to be not statistically significant will be reported as being inconclusive. Based on the nature of our study design, we assume missing data to be minimal, where linear mixed effect model is robust to handle such missing value situations without creating any obvious bias. For all the result tables of statistical analysis, statistical estimates of population parameters will be tabulated along with corresponding confidence intervals (CIs). Given the lack of any comparable study in the literature, we performed a power analysis guided by the number of participants we are able to enroll based on the size of the grant. Briefly, with a sample of N=20 participants, we will be able to detect an effect size of $d_z = 0.66$ with $\alpha = 0.05$ and $\beta = 0.2$. Power analysis was performed with G*Power.

Questionnaire data

The level of trait anxiety, as indicated by the STAI form Y-2, will be compared to the participant's corticospinal excitability to investigate whether a correlation between the two factors exists. Lower motivation, as measured by the BIS/BAS, is hypothesized after glucose consumption as compared to after water consumption. Greater state anxiety, as measured by the STAI form Y-1, is hypothesized after glucose consumption as compared to after water consumption. Greater negative affect and lesser positive affect, as measured by the PANAS, is hypothesized after glucose consumption as compared to after water consumption.

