4 BASIC STUDY DESIGN

Participants who pass an initial screening by phone are asked to attend a screening visit where consent is provided, eligibility for study participation is confirmed and demographic information is collected. Participants who are eligible to participate will then be asked to return for two study sessions after an MRI scan. Sessions will start at 8.00 am and study participants will be asked to fast for the preceding 12 hours and to consume approximately 150g of carbohydrates each day for the 3 days prior to the session. The study procedures are identical for both study visits. The order of the two sessions is equally randomized across participants.

In one visit, an oral 3-hour GTT with a 75g load of glucose will be administered. In the other visit, pure drinking water will be used. Both study visits have the following time-line:

1. Determined the target (hand area of the left precentral gyrus, left primary motor cortex) based on MR images using a TMS neuro-navigation system.
2. Fitting of an EEG electrode net.
3. Baseline EEG and MEP measurements elicited by TMS
4. Measurement of fasting blood glucose level by finger prick
5. Administration of drink (glucose drink or water, 296mL of H₂O for both drinks)
6. Capillary blood draw (finger prick) for glucose level testing and TMS-induced EEG and MEP measurements at 0, 30, 60, 120, 180 minutes after drink administration
7. Digitization of EEG electrodes on the scalp using a camera-type scanner

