4.1 TREATMENT ASSIGNMENT PROCEDURES

Each participant will experience two experimental conditions (glucose drink and water). There are 2 ways to order the two conditions (glucose drink and then water, water and then glucose drink). By randomization, each participant will be assigned to one of the sequences. Ten participants will be assigned to each of these 2 sequence groups. Each session has at least a 3-day gap to minimize the presence of outlasting effects of either the GTT or the TMS. The randomization schedule will be computed prior to recruitment of subjects and the random assignments will be concealed from the personnel who screen potential participants until the moment that the participant is enrolled and ready for baseline evaluations. To accomplish this, the randomization schedule will be used to create a set of sequentially-numbered opaque sealed envelopes.

- Glucose drink → Drinking water (10 participants)
- Drinking water → Glucose drink (10 participants)

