11.2 CHOICE OF SAMPLE SIZE

The choice of sample size was based on expert opinion and funding limit; we conjecture that 20 participants may be sufficient to provide adequate precision for the estimators of variance components and other parameters for which information is needed to plan a future study. As a rough and indirect assessment of the precision afforded by studying a sample of 20 subjects, we considered that an estimate of the proportion of subjects in the target population that would experience a greater decrease in MEP and TEP amplitude with verum-GTT (Glucose), relative to control-GTT(water) for an observed estimate of 50%, the 95% confidence interval would span [50% ± 20%]. Or, if 80% was the observed estimate, then the 95% CI would span [80% ± 16%].

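### The primary crossover model in 11.1 has no session (period) term; adding one is a cheap, minor improvement, mainly for the variance estimates wanted from this pilot

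*Combined protocol and SAP*

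**What the plan says.** Section 4 describes two visits with the same procedures, one with glucose and one with water: "The order of the two sessions is equally randomized across participants". Section 4.1 fixes the numbers: "Ten participants will be assigned to each of these 2 sequence groups". Sessions are three or more days apart.

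Section 11.1 analyses changes: "For all analyses, outcome measures are analyzed as the difference from baseline metrics before the GTT". The mixed model has "baseline measures (continuous), time of measures (categorical), treatment method (binary) and time by treatment as fixed effects", a random intercept and an AR(1) structure over 0 to 180 minutes. The primary result is the two-sided Wald test of treatment, and no degrees-of-freedom method is named. Neither session, period, order nor sequence appears in this model or anywhere else in the analysis plan.

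On sample size, 11.1 says "we performed a power analysis guided by the number of participants we are able to enroll based on the size of the grant" and gives a detectable d_z of 0.66 for N = 20, alpha 0.05 and beta 0.2. Section 11.2 adds: "The choice of sample size was based on expert opinion and funding limit". It conjectures that 20 participants may provide "adequate precision for the estimators of variance components and other parameters for which information is needed to plan a future study". Under 9.4, the data of a participant who drops out are left out of the analysis.

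**The concern.** Session order is a randomised design factor and is known for everyone, but the model ignores it. Suppose the post-drink change differs between session 1 and session 2, for example because participants are more used to the procedure. That difference enters the glucose-minus-water contrast with one sign in the glucose-first sequence and the opposite sign in the water-first sequence. With equal sequences it cancels in the mean but not in the spread, so it is counted as random variation.

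At stake are the variance components that 11.2 wants for planning, and the CIs that 11.1 says will be tabulated. If exclusions leave unequal sequences, the cancellation is also incomplete.

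**Working it through.** **1. Inputs.** From 11.1: N = 20, d_z 0.66, two-sided alpha 0.05, power 0.80. From 4.1: sequences 10:10. The documents give no size for a session difference, so it is assumed: π = 0.1, 0.25 or 0.5, in SDs of the within-person glucose-minus-water difference D.

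**2. The plan's own figure.** Paired t, noncentrality 0.66 × √20 = 2.95, df 19, critical value 2.093: power 0.7995, and detectable d_z at 80% power 0.6604. The stated 0.66 reproduces.

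**3. Paired-t approximation.** With SD 1 within sequence, D has mean τ − π (glucose first) or τ + π (water first). Without a session term, the 20 offsets of ±π add 20π² to the sum of squares, so E(s²) = 1 + (20/19)π². The SE ratio is √E(s²). The follow-up N gives 80% power at 0.66/√E(s²). Power is simulated, with 400,000 data sets per shift.

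| π | E(s²) | SE ratio | Power without term | Follow-up N |
|---|---|---|---|---|
| 0 | 1.00 | 1.00 | 79.9% | 21 |
| 0.1 | 1.01 | 1.01 | 79.6% | 21 |
| 0.25 | 1.07 | 1.03 | 78.1% | 22 |
| 0.5 | 1.26 | 1.12 | 72.2% | 25 |

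With the term (df 18, critical value 2.101), power is 0.797 at every shift and detectable d_z is 0.662. Simulated type I error at π = 0.5 is 0.030 without the term and 0.051 with it. The analysis without the term is valid but wider than it need be.

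**4. Unequal sequences.** Without the term, the bias is π × |n1 − n2|/(n1 + n2). At 10:9 this is 1/19 = 5% of the shift; at 10:8 it is 2/18 = 11%. At 10:8 the bias is 0.028 SD (π = 0.25) or 0.056 SD (π = 0.5), against an SE of 1/√18 = 0.236 SD.

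**5. Variance components against known values.** REML fits, 300 simulated trials, no baseline covariate, true residual variance 1, subject variance 1, AR(1) correlation 0.5, and π = 0.5:

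| | True | Without term | With term |
|---|---|---|---|
| Residual variance | 1 | 1.124 | 1.024 |
| Subject variance | 1 | 0.940 | 0.978 |
| AR(1) correlation | 0.5 | 0.548 | 0.505 |

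**6. The 11.1 model with a baseline covariate.** REML, z-based Wald test, 10:10, 1,500 trials per setting. Assumed: subject SD 1, residual SD 1 with AR(1) correlation 0.3, session-level SD 0.5, baseline error SD 0.5, and session-specific SD of the change 0 (setting A) or 0.7 (setting B). At π = 0.5:

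| | A without | A with | B without | B with |
|---|---|---|---|---|
| Actual SD of estimate | 0.2247 | 0.2245 | 0.3146 | 0.3140 |
| Mean reported SE | 0.2148 | 0.2008 | 0.2929 | 0.2631 |

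The actual precision is the same with and without the term. The with-term SE is too small: 0.2008/0.2245 = 0.89 in A and 0.2631/0.3140 = 0.84 in B. With no shift, type I error without and with the term is 0.089 and 0.090 (A), and 0.115 and 0.118 (B), so the omitted session term is not the cause. At π = 0.5 without the term it is 0.066 (A) and 0.076 (B), because the inflated residual hides part of the excess. In two separate refits at that shift, adding the term moved 95% coverage from 93.5% to 91.5% and from 91.7% to 90.0% in A, and from 93.2% to 90.2% and from 89.7% to 86.8% in B.

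**The case against.** The design already limits the problem. A shift that moves baseline and post-drink values together is largely absorbed by the change score and the baseline covariate. Section 4 fixes the fast, the 8 am start and the procedures, and section 5 keeps one researcher per participant. Allocation is balanced and 11.1 expects few missing data. Nothing in the documents points to a session difference in the change, and a visible effect needs about 0.5 SD, three quarters of the detectable d_z (0.5/0.66 = 0.76). All of this stands, and it keeps the point minor.

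Sampling error also exceeds the distortion. A variance on 19 df has a 95% CI of 0.58 to 2.13 times its estimate, against a 7% overstatement at π = 0.25. In settings A and B, the subject variance estimate varied between trials with an SD of 0.10 and 0.19, while omitting the term at π = 0.5 moved it by 0.089 − 0.068 = 0.021 and 0.207 − 0.146 = 0.061. This stands too. The distortion is systematic, however, and can be removed at almost no cost.

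A reader might infer that the planned mixed model loses power. At π = 0.5 the REML fits do reject less often without the term (0.793 against 0.817 in A, 0.859 against 0.897 in B). This cannot be read as a true power loss, because the tests compared have different type I error and the estimate's SD is the same.

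**Conclusion.** The omission is certain; its effect is conditional on a session difference in the post-drink change that the documents do not quantify. If there is one, the residual variance is overstated and the between-subject variance understated, and a valid paired analysis gives a wider CI: about 3% wider at 0.25 SD and 12% at 0.5 SD, with almost no effect at 0.1 SD. The percentages for the paired difference rest on the paired-t approximation, and those for the mixed model on the assumed variances.

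Two stronger readings are not supported. One is that the primary estimate is biased: at 10:10 it is not, and at 10:8 the bias is at most about a quarter of one SE over the shifts considered (0.056/0.236 = 0.24). The other is that the missing term makes the planned test anti-conservative: the simulated excess is there with no shift, with or without the term. Its likely sources are the lack of a session-level random term and the z reference distribution; 11.1 names no df method. Severity: minor, a cheap improvement.

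**What to change.** Before data are seen, add session (1 or 2) as a fixed effect to the 11.1 model for MEP, TEP, theta and alpha, and report its estimate with its CI. In the same change, add a subject-by-session random effect and name a small-sample df method, so that the session term does not merely remove the accidental slack shown above. The simulations did not test this full combination. The paired-t version with a session term, which works on one difference per person, held its level (0.051 at π = 0.5).

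The questionnaire part of 11.1 names no model for the glucose-versus-water comparisons, so nothing is omitted there; the same term can be used in whatever model is chosen.

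The cost is one fixed-effect term, one variance parameter and no new data. In the paired-t approximation with no shift, the session term takes power from 79.9% to 79.7% at 10:10, and from 75.2% to 74.3% at 10:8.

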5.2 STUDY SESSIONS

- MRI scan (Visit 2)

We will ask participants to come in and complete an MRI scan. MRI scan imaging will take place at the Biomedical Research Imaging Center (BRIC), located on the first floor in Marsico Hall. Screening questions will be completed prior to the MRI scan (attached) and all preparations for the scan will take place in a facility area behind a locked door, where only research study personnel have access. When subjects are required to change their clothing, they will be allowed to do so alone, in a room with a door that locks. MRI scan will be performed by trained study personnel or designees of the PI that are approved to complete an MRI scan.

- Study sessions (Visit 3-4)

All participants will undergo two study sessions (glucose or water administration) with at least 3-day gap to minimize the effect of either GTT or TMS. In each visit, all participants will be asked to fill out the questionnaires at the beginning and end of the session. Participants undergo a two-minute eyes-open resting-state EEG recorded with high-density, 128 channels EEG system (Netamps 410, Electrical Geodesics Inc, EGI) using Geodesic Sensor Nets (sampled at 1000 Hz). EEG nets will be fitted at the beginning of the two study visits and remain in place until completion of the study visit. Also, participants will perform a cognitive control task to investigate if changes in glucose blood level could modulate cognition.

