Single-pulse TMS on the motor cortex leads to a twitch in the target muscle evoking a motor-evoked potential (MEP) measured by electromyography (EMG) electrodes. Participants will be seated in a comfortable armchair with their hands positioned on the armrest. Two disposable electrodes (15x21mm, Ambu Neuroline) will be placed in a tendon-belly arrangement over the first dorsal interosseous muscle and a ground electrode will be placed over the styloid process of the ulna. A figure-eight coil (C-B60, MagVenture) will be used for stimulation and EMG signals will be recorded by an amplifier (MagPro X100, MagVenture). The coil will be placed tangentially over the scalp with the handle pointing backwards and laterally at 45° from the mid-sagittal line. Biphasic TMS pulses will be applied over the motor cortex and the resting motor threshold (RMT) will be defined by the minimum TMS intensity required to evoke MEP of at least 50 uV in 50% of 10 consecutive trials. At baseline, 10 TMS pulses will be applied on the scalp and EEG and EMG data will be collected. At the same time, blood glucose level will be measured by 5uL of finger prick blood sampling as a baseline glucose level. In an intervention step, we will administer a 75g load of glucose drink or drinking water at each study visit. After then, glucose level testing and EMG/EEG data collection will be performed at 0, 30, 60, 120, and 180 minutes after the drink administration. Once participants complete the first study visit, a study coordinator will schedule their next visit with at least 3-day gap.

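### Section 11.1: with one intercept per participant, the standard error of the time-averaged drink effect can be too small, and neither the contrast nor its df is defined

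*Combined protocol and SAP*

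**What the plan says.** The trial is a two-period crossover. Section 4.1: "Each participant will experience two experimental conditions (glucose drink and water"). Section 5.2 puts the drinks on different days, "All participants will undergo two study sessions (glucose or water administration) with at least 3-day gap", and each session has one baseline: "At baseline, 10 TMS pulses will be applied on the scalp and EEG and EMG data will be collected".

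On the analysis, section 11.1 says:

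- The scale is change: "outcome measures are analyzed as the difference from baseline metrics before the GTT". The fixed effects are baseline, time, drink and drink by time.
- The primary test is given as follows: "The two sided Wald-test of treatment method (fixed effect) between the verum GTT versus control GTT condition is our primary result of interest". The stated hypothesis is a main effect of drink with no interaction.
- The random part of the model concerns "the within-subject effect among different time point (0, 30, 60, 120, 180 minutes"), and the plan has this effect "modeled as random intercept assuming autoregression model (AR(1)) as covariance structure".

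It does not name the unit to which the intercept belongs, a participant-by-session effect, the df or reference distribution of the Wald test, or the contrast that represents the drink effect when the interaction is also in the model. The power statement in the same section is a detectable d_z of 0.66 with N = 20, alpha 0.05 and beta 0.2.

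**The concern.** The drink comparison rests on 20 between-session differences, not on 20 × 2 × 5 = 200 readings. An intercept per participant removes what all ten readings of a person share. What the five change scores of one session share, and the other session does not, can then be carried only by the AR(1) term. AR(1) correlation fades with lag, so it absorbs only part of an error that stays constant from 0 to 180 minutes.

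Such error has two plausible sources: a day-to-day shift that the baseline does not fully remove, and the noise of the session's one baseline, which enters all five scores. If the model under-counts it, the primary test rejects too often and the tabulated confidence interval is too narrow. A normal reference for the Wald statistic would add to this.

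**Working it through.** **1. The plan's own figure.** Paired t-test, n = 20, 19 df, two-sided 0.05: noncentrality 0.66 × √20 = 2.95, critical value 2.093, power 0.799. The figure is reproduced. It treats the participant's between-session difference as the unit.

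**2. The reference distribution alone.** With a correct standard error, P(|t(19)| > 1.96) = 0.065.

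**3. What a session's five scores share.** Write a post-drink reading as person + S + e and the baseline as person + S + n, where S is the session shift and n the baseline noise. If b is the fitted slope of the post-drink level on baseline, the five scores share (1 − b)S − bn, with variance (1 − b)² × var(S) + b² × var(n). Assumed: var(n) = residual variance = 1, independent residuals, and the mean fitted b from the simulations in step 4.

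| var(S) | b | Shift part | Baseline-noise part |
|---|---|---|---|
| 0.25 | 0.39 | 0.61² × 0.25 = 0.09 | 0.39² = 0.15 |
| 0.5 | 0.50 | 0.50² × 0.5 = 0.13 | 0.50² = 0.25 |
| 1 | 0.61 | 0.39² × 1 = 0.15 | 0.61² = 0.37 |

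Baseline noise is the larger part in each row.

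**4. Simulation under no drink effect.** From the documents: 20 people, 2 sessions, 5 times, change from baseline, and the four fixed effects. Assumed: residual, between-person and baseline-noise variance all 1; session variance as shown, with the shift also present at baseline. The model has a participant intercept plus AR(1) by visit order within session, fitted by REML, and the test is of the drink effect averaged over the five times. There were 4,000 trials per scenario (Monte Carlo error 0.3–0.5 points). Each cell gives the ratio of mean SE to true SE, then type I error on t(19) / on z.

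| Session variance | No serial correlation | 0.4 per 30 min, baseline correlated too | 0.4 per 30 min, baseline uncorrelated |
|---|---|---|---|
| 0 | 0.93; 5.1% / 7.2% | 0.98; 4.6% / 6.2% | 0.94; 5.6% / 7.4% |
| 0.1 | 0.88; 7.7% / 9.3% | 0.93; 6.1% / 7.1% | 0.91; 6.9% / 8.7% |
| 0.25 | 0.81; 9.4% / 12.0% | 0.91; 6.7% / 8.8% | 0.90; 7.2% / 8.8% |
| 0.5 | 0.79; 9.9% / 12.4% | 0.90; 7.6% / 9.5% | 0.87; 8.0% / 10.3% |
| 1 | 0.76; 12.1% / 14.1% | 0.88; 7.6% / 9.6% | 0.85; 8.7% / 11.1% |

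A separate run of 2,000 trials at session variance 0.25–1 gave 6.1–7.2% (t19) and 7.7–9.3% (z) with correlation 0.4, and 9.3–11.7% and 11.4–14.4% with none.

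**5. Which error matters.**

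- Purely serial error (AR(1) 0.5, no session effect) with AR(1) fitted within session: SE ratio 0.98, 4.9% on t(19), 6.5% on z.
- Almost noise-free baseline (variance 0.01), session variance 0.5, shift already present at baseline: ratio 0.97, 5.1% on t(19).
- Same baseline, shift arising only after the drink: ratio 0.81 and 10.7% (session variance 0.25, independent residuals); ratio 0.85 and 9.0% (0.5, correlation 0.4).

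The shortfall therefore comes from constant error that the baseline does not remove, including error that the baseline adds.

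**6. Which contrast.** With drink by time in the model and time 0 as reference level, the treatment coefficient is the drink effect at time 0. For that coefficient the participant-only model gave about 3–6.5% on t(19). It does not answer the stated main-effect question.

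**7. Alternatives in the step 4 scenarios.** Participant plus participant-by-session intercepts with Satterthwaite df: 3.9–6.0%. Baseline-adjusted paired regression on 18 df: 4.3–5.4%, with intervals 0.83–1.04 times as wide as those of the two-intercept model.

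**The case against.** The plan already does much of the work. It subtracts each session's baseline, adjusts for it and adds AR(1). What remains depends on session variance, baseline noise and serial correlation, none of which the documents give. With correlation 0.4 and t(19), the excess over 5% is about 1 to 4 points. The trial is a declared pilot whose size was set partly by funding. All of this stands. It limits the size of the point, but does not supply the missing contrast, grouping or df.

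A reader might infer four stronger things that the documents do not support:

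- *Any error shared within a session makes the standard error too small.* Not so: AR(1) handles purely serial error (step 5).
- *The grouping is so open that the result could as easily be too conservative.* An intercept per session would make the standard error 5–25% too large (1.9–5.2% on z). That reading rests only on the list of five times, which both sessions share. The term within-subject and a power statement on 20 participants point to the participant.
- *The power figure is wrong.* It is correct for a paired comparison.
- *The plan fails its own aim in section 11.2*, which wants "adequate precision for the estimators of variance components and other parameters for which information is needed to plan a future study". That section names no between-session component, and a later paired crossover can be planned from the SD of within-person differences.

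**Conclusion.** The point holds in a limited form and is worth settling before analysis. On its natural reading, the section 11.1 model understates the standard error of the time-averaged drink effect when a session carries roughly constant error that baseline adjustment does not remove.

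At session variance 0.25–1 times residual variance, with between-person variance and baseline noise equal to residual variance, the standard error is 9–15% too small with serial correlation 0.4 per 30 minutes. It is 19–24% too small with none, which is the extreme case. Type I error is about 6–9% (t19) or 8–11% (z) in the first case, and 9–12% or 11–14% in the second. With no session variance the test is near 5% on t(19). These sizes are conditional on assumptions and apply only to the time-averaged contrast. What needs no assumption is that the plan states neither that contrast nor the df of its primary test.

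**What to change.** In section 11.1, define the primary test as the drink contrast averaged over the five post-drink times. Then choose one of these in advance:

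- (a) For each participant, take the between-session difference in mean change, regress it on the difference between the two baselines, and test the intercept on 20 − 2 = 18 df. This matches the paired basis of the power statement.
- (b) Fit random intercepts for participant and for participant by session, with AR(1) within session, the baseline covariate kept, and Kenward-Roger or Satterthwaite df. Name (a) as the fallback if the session variance is estimated at zero.

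An unadjusted paired t-test on change scores is not a good substitute. Its true SE was 0.320–0.368, against 0.144–0.293 for (a), because it discards the baseline adjustment.

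The cost is one or two sentences and no change to data collection. Under (b), intervals are about 14–37% wider than with the participant-only z analysis over the assumed range. If session variance is truly zero, they are 7–15% wider than participant-only on t(19), and the test is slightly conservative (3.9–4.5%). With five readings per session, (b) can also reach the boundary: with correlation 0.4, a check put the session variance at practically zero in about 12% of trials at a true value of 0.25, 7% at 0.5, and 22% at 0.5 with lower baseline noise. Option (a) needs both sessions and a rule for a missing reading.
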